4.2.1.1.2 Maximum Intensity

Maximum overall intensity is derived from the daily intensities computed as described in Section 4.2.1.1.1 and is calculated as the maximum of the daily intensities over the period considered.

4.2.1.1.3 Presence

Presence is derived from the maximum overall intensity over the time period considered:

- None: No presence
- Grade 1, Grade 2, or Grade 3: Presence
- Missing or Unknown: Missing presence

Participants with at least one non-missing presence for a specific endpoint will be included in the analysis. Conversely, those without a non-missing presence will not be included in the analysis of the endpoint.

The time period is displayed as D1-D4, D5-D8, D9 and later.

4.2.1.1.4 Time of Onset

Time of onset is derived from the computed daily intensities computed as described in Section 4.2.1.1.1. It corresponds to the first day with intensity of Grade 1, Grade 2, or Grade 3. It corresponds to the first day with intensity of Grade 1, Grade 2, or Grade 3.

Note: If a reaction is not continuous (i.e., reaction occurs over two separate periods of time intervened by at least one daily intensity Missing or None) then the time of onset is the first day of the first occurrence.

Time of onset period is displayed as, D1-D4, D5-D8.

4.2.1.1.5 Number of Days of Presence During the Solicited Period

Number of days of presence over the period considered is derived from the daily intensities computed as described in Section 4.2.1.1.1. It corresponds to the number of days with daily intensities of Grade 1, Grade 2, or Grade 3. Number of days of presence on the solicited period with a specified intensity may also be derived.

4.2.1.1.6 Overall Number of Days of Occurrence

If a reaction is ongoing at the end of the solicited period, then the overall number of days of presence is derived from the daily intensities and the end date of the reaction after the end of the solicited period. The overall number of days of presence is:

(End date - last vaccination date) + (number of days of presence within the solicited period) - length of the solicited period + 1

If the end date is missing or incomplete (contains missing data), the overall number of days of presence will be considered as Missing.

4.2.1.1.7 Ongoing

Ongoing is derived from the last daily intensity of the solicited period computed as described inSection 4.2.1.1.1 and the maximum intensity on the ongoing period. The investigator's ongoing flag is not used because the measurement would determine the ongoing status of the reaction. *Note the intensity could be considered None (not a reaction) in the analysis despite being considered a reaction by the investigator (e.g., swelling measurement > 0 mm but < 25 mm in adults).*

- Ongoing: if the last daily intensity of the solicited period is at least Grade 1 and the maximum intensity on the ongoing period is at least Grade 1
- Not ongoing: if the last daily intensity of the solicited period is None or the maximum intensity on the ongoing period is None.
- Missing: all other conditions (in this case, it is not included in the denominator of the ongoing analysis in the safety tables).

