3.4.4 Handling of Missing Data and Outliers

3.4.4.1 Safety

Generally, no replacement will be done for Safety Missing Data and Outliers.

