4.2 Complementary Information on Derived Endpoints: Calculation Methods

4.2.1 Safety

4.2.1.1 Solicited Reactions

4.2.1.1.1 Daily Intensity

All daily records for solicited reactions will be derived into daily intensity according to the following classification: None, Grade 1, Grade 2, Grade 3, or Missing (Unknown).

For the derivation of daily intensities, the following sequential steps will be applied:

- 1. Solicited reactions (except Fever/Pyrexia) with CRF presence recorded as "No" and with all daily records missing (Unknown) then all daily intensities will be derived as None.
- 2. For non-measurable solicited reactions, daily intensities will correspond to daily records reported in the clinical database. For measurable solicited reactions the daily measurements reported in the clinical database will be converted based upon the intensity scales defined in the protocol; this assumes a reaction that is too large to measure (non-measurable, "NM") is Grade 3. Note the intensity could be considered "None" (not a reaction) in the analysis despite being considered a reaction by the investigator (e.g., swelling measurement > 0 mm but < 25 mm in adults).

Note: The maximum intensity on the ongoing period is derived from the record of the maximum intensity/measurement after the end of the solicited period following the rule described above.

Table 4.1: Solicited injection site reactions: terminology, definitions, and intensity scales – Infants and toddlers aged ≤ 23 months

CRF term (MedDRA	Injection site tenderness	Injection site erythema	Injection site swelling
lowest level			
term [LLT])			
Diary card	Tenderness	Redness	Swelling
term			
Definition	mobilized	including the approximate point of needle entry	Swelling at or near the injection site Swelling or edema is caused by a fluid infiltration in tissue or cavity and, depending on the space available for the fluid to disperse, swelling may be either soft (typically) or firm (less typical) to touch and thus can be

			best described by looking at the
			size of the swelling
Intensity	Grade 1: Minor reaction when	Grade 1: > 0 to < 25 mm	Grade 1: > 0 to < 25 mm
scale*	injection site is touched	Grade 2: \geq 25 to	Grade 2: \geq 25 to \leq 50 mm
	Grade 2: Cries or protests	< 50 mm	Grade $3: \ge 50 \text{ mm}$
	when injection site is touched	Grade $3: \ge 50 \mathrm{mm}$	
	Grade 3 (CRF): Cries when		
	injected limb is mobilized, or		
	the movement of the injected		
	limb is reduced		

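### The SAP's ongoing rule drops a solicited reaction graded on D8 with no later intensity record, even when the flag or end date shows it had stopped

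*SAP*

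**What the plan says.** SAP 4.2.1.1.7 has three classes.

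- *Ongoing* requires that "the last daily intensity of the solicited period is at least Grade 1 and the maximum intensity on the ongoing period" is also at least Grade 1.
- The second class reads "Not ongoing: if the last daily intensity of the solicited period is None or the maximum intensity on the ongoing period is None". Either condition is enough.
- The third takes the rest: "Missing: all other conditions (in this case, it is not included in the denominator of the ongoing analysis in the safety tables".

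The post-D8 value comes from a single source, given in SAP 4.2.1.1.1: "The maximum intensity on the ongoing period is derived from the record of the maximum intensity/measurement after the end of the solicited period". The SAP does not say whether None, zero or nothing is entered there when a reaction ended on D8.

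The site's own judgement is set aside: "The investigator's ongoing flag is not used because the measurement would determine the ongoing status of the reaction".

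Two other provisions bear on a blank field. SAP 4.2.1.1.1 converts blanks to None only for reactions other than fever whose CRF presence is No and "with all daily records missing (Unknown) then all daily intensities will be derived as None". SAP 3.4.4.1 adds: "Generally, no replacement will be done for Safety Missing Data and Outliers".

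**The concern.** A reaction that is Grade 1 to 3 on D8 and gone on D9 may leave nothing to record after D8. If the field is then blank, neither of the first two classes applies, and the reaction is *Missing* and leaves the denominator. A reaction that persists does produce a post-D8 intensity and stays in. Whether a D8 reaction is analysed would then depend on whether it persisted, which is the outcome being described, and the ongoing percentage would be too high.

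The site may have recorded that the reaction stopped, but the rule does not use that record. The reason given, that the measurement decides, suits erythema, swelling and fever, where a small measurement can fall below the grading threshold. It does not suit reactions with no measurement, such as pain, tenderness, headache, malaise, myalgia and irritability.

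**Working it through.** The plan states no figure that depends on this rule, so there is none to reproduce. The check applies the three classes to every combination of inputs and then sizes the effect.

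**Step 1. All combinations under SAP 4.2.1.1.7.**

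| D8 intensity | Post-D8 maximum: None | Post-D8 maximum: Grade 1+ | Post-D8 maximum: blank |
|---|---|---|---|
| None | Not ongoing | Not ongoing | Not ongoing |
| Grade 1+ | Not ongoing | Ongoing | **Missing** |
| Blank | Not ongoing | Missing | Missing |

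The concern sits in the bold cell only. A graded D8 followed by a recorded None is correctly *Not ongoing*. Everyone with None on D8 stays in the denominator.

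**Step 2. Does any other rule rescue the bold cell?**

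- The blank-to-None step in 4.2.1.1.1 needs every daily record to be missing, so it cannot apply to a reaction graded on D8.
- SAP 3.4.4.1 generally rules out replacement.
- The flag is not used.
- The end date enters 4.2.1.1.6 for counting days, but not the classification in 4.2.1.1.7.

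Nothing in the SAP reaches the cell.

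**Step 3. Size.** Let N be the participants analysed, r those with the reaction on D8, o those of them who continue past D8, and b the share of the r − o resolved reactions whose post-D8 field is blank. Everyone else is taken to have a known status.

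- Under the rule: o / (N − b(r − o))
- With resolved reactions counted as *Not ongoing*: o / N

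The numerator is the same in both. N comes from the documents: 223 enrolled and 200 evaluable per main age category, and a minimum of 20 enrolled in each older age subgroup. The values of r, o and b are assumptions.

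| N | r | o | b | Under the rule | Resolved counted |
|---|---|---|---|---|---|
| 223 | 10 | 4 | 1 | 4/217 = 1.84% | 4/223 = 1.79% |
| 200 | 20 | 8 | 1 | 8/188 = 4.26% | 8/200 = 4.00% |
| 200 | 20 | 8 | 0.5 | 8/194 = 4.12% | 4.00% |
| 200 | 20 | 8 | 0 | 8/200 = 4.00% | 4.00% |
| 200 | 40 | 16 | 1 | 16/176 = 9.09% | 16/200 = 8.00% |
| 20 | 4 | 2 | 1 | 2/18 = 11.1% | 2/20 = 10.0% |

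**Step 4. Dependence on the denominator.** Take the case r = 20, o = 8.

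- Restricted to participants with the reaction on D8: 8/8 = 100% if all 12 resolved reactions are blank and 8/14 = 57% if half are, against 8/20 = 40%.
- Restricted to participants with the reaction at any time in the week, say 40 of them: 8/28 = 28.6% against 8/40 = 20.0%.

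SAP 4.2.1.1.7 says only that *Missing* cases are removed. It names neither restriction.

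**The case against.** The strongest defence is that the rule already provides for a reaction that stops: a recorded None after D8 gives *Not ongoing*. The CRF is not in the documents, and if sites enter None there is no bias at all. On the denominator the rule implies, the examples above differ by about 1.1 percentage points at most, in a study that tests no hypotheses. Ongoing status is not among the endpoint attributes listed in SAP Table 2.1 or 3.4.3, and the days of presence within D1 to D8 (4.2.1.1.5) are unaffected. All of this stands, and it makes the point minor. It does not close the gap: the SAP neither states the recording convention nor says what to do when the field is blank. Using a recorded flag or date is not replacement of missing data either, since the information was collected.

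Three stronger readings are tempting, and the documents do not support them.

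- *Nearly every classifiable D8 reaction counts as ongoing (100% against 40%).* This needs both a blank-field convention and a denominator of D8 reactions. The documents give neither.
- *A blank D8 followed by a later graded record should be Ongoing.* Continuation and new onset cannot be told apart here, and Protocol 10.2.1 makes a solicited term that starts after the solicited period an unsolicited event. *Missing* is defensible.
- *The last display row is distorted in the same way.* SAP 4.2.1.1.3 says "The time period is displayed as D1-D4, D5-D8, D9 and later", but it admits participants by endpoint. On the natural reading, anyone with a known status in D1 to D8 stays in.

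**Conclusion.** The concern holds as a conditional, low-severity defect. The text puts a reaction graded on D8 with no post-D8 intensity record into *Missing* and out of the denominator, whatever the flag or end date shows. The upward bias follows if two assumptions hold: the CRF leaves that field blank when a reaction has ended, and persisting reactions do have their later intensity recorded. Counting all participants with a known status, the overstatement in the assumed examples runs from 0.05 points (1.84% against 1.79%) to about 1.1 points. It becomes large only on a narrower denominator that the SAP does not state. The number classed as ongoing does not change in any of these cases.

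**What to change.** In SAP 4.2.1.1.7, add one rule for a D8 intensity of at least Grade 1 with no post-D8 intensity record: classify the reaction as *Not ongoing* if the investigator's ongoing flag is No or the end date is on or before D8. Keep *Missing* for that combination only when neither is available. Where a post-D8 measurement is recorded, let it override the flag, as now. State the denominator of the ongoing analysis explicitly.

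The cost is a few lines of SAP text and a small programming change, with no new data collection. The SAP already refers to both the flag and end dates. It mentions end dates only for reactions that outlast the solicited period, so the flag may have to carry most cases. The downside is that flag and end date need the usual consistency check against each other and against the recorded intensities.

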4.2.1.2 Unsolicited AEs

4.2.1.2.1 Presence

An observation will be considered an event if it has at least a verbatim term and is not a Grade 0 intensity event.

Grade 0 events are not included in safety analysis but are included in separate listings.

4.2.1.2.2 Intensity

Intensity will be derived according to the following classification: None, Grade 1, Grade 2, Grade 3, or Missing.

If the unsolicited AE is measurable and its preferred term is part of the list of solicited reactions, then the measurement is derived based upon and following the same rule of the intensity scales defined in the protocol for that measurable injection site or systemic reaction. Note the intensity could be considered as "None" (not a reaction) in the analysis despite being considered a reaction by the investigator (e.g., swelling measurement >0 mm but < 25 mm in adults).

Intensity for the other unsolicited AEs will correspond to the value reported in the CRF.

The maximum intensity corresponds to the highest intensity for a unique term.

4.2.1.2.3 Last Vaccination

Last vaccination before an unsolicited AE is derived from the start date of the unsolicited AE provided in the CRF and is calculated as follows:

- If an unsolicited AE has a complete start date and different to any of the vaccination dates, the start date is used to determine the last vaccination before the unsolicited AE.
- If an unsolicited AE has a partially missing start date and there is clear evidence about the last vaccination from the partially missing start date, then the start date is used to determine the last vaccination before the unsolicited. Situations may happen as:
 - o If the start date of AE has missing Day and non-missing Month and Year
 - If the "Month/Year of vaccination (i) date" < "Month/Year of AE start date" < "Month/Year of vaccination (i+1) date", then it is clear that the last vaccination before this unsolicited AE is the vaccination i.
 - If the "Month/Year of vaccination (i) date" < "Month/Year of AE start date" and there is no injection (i+1), then it is clear that the last vaccination before this unsolicited AE is the vaccination i.
 - o If the start date of AE has missing Day and Month and non-missing Year:
 - If the "Year of vaccination (i) date" < "Year of AE start date" < "Year of vaccination (i+1) date", then it is clear that the last vaccination before this unsolicited AE is the vaccination i.
 - If the "Year of vaccination (i) date" < "Year of AE start date" and there is no injection (i+1), then it is clear that the last vaccination before this unsolicited AE is the vaccination i.
- If the start date is missing or partially missing (with no clear evidence about the last vaccination), or equal to any vaccination date, then the visit number in the "Appeared after Visit" or similar field, is used to determine the last vaccination before the unsolicited AE.

4.2.1.2.4 Time of Onset

Time of onset is derived from the start date of the unsolicited AE and the date of last vaccination as described in Section 4.2.1.2.3:

Time of Onset = start date of the unsolicited AE - date of last vaccination before the unsolicited AE + 1

The time of onset is considered as missing only if one or both dates are missing or partially missing.

The unsolicited AEs will be analyzed "Within 30 days" after each vaccination, which corresponds to AEs with a time of onset between 1 and 31 days

Unsolicited AE that occurred before vaccination (negative time of onset) will not be included in analysis but will be listed separately.

- For unsolicited AE with missing day, month and year, the unsolicited AE will be classified as "Within 30 days"
- For unsolicited AE with partially missing start date, the partial available information will be used to determine if this AE is classified "Within 30 days" or "Not within 30 days". An AE will be categorized as "Not within 30 days" only if there is clear evidence from the partially missing start date that this AE happens before the first vaccination or after the last vaccination + 30 days. In all other situations, this AE is considered as "Within 30 days". Situations may happen as:
 - o If the start date of AE has missing Day and non-missing Month and Year
 - If the "Month/Year of AE start date" < "Month/Year of first vaccination date", then it is clear that this unsolicited AE happened before the first vaccination and this unsolicited AE will not be included in the analysis but will be listed separately.
 - Else if the "Month/Year of last vaccination date" <= "Month/Year of AE start date" <= "Month/Year of (last vaccination date + 30 days)", then this unsolicited AE will be categorized as "Within 30 days".
 - Else if the "Month/Year of AE start date" > "Month/Year of (last vaccination date + 30 days)", then this unsolicited AE will be categorized as "not within 30 days".
 - o If the start date of AE has missing Day and Month and non-missing Year:
 - If the "Year of AE start date" < "Year of first vaccination date", then it is clear that this unsolicited AE happens before the first vaccination and this unsolicited AE will not be included in the analysis but will be listed separately.
 - Else if the "Year of last vaccination date" <= "Year of AE start date" <= "Year of (last vaccination date + 30 days)", then this unsolicited AE will be categorized as "Within 30 days".
 - Else if the "Year of AE start date" > "Year of (last vaccination date + 30 days)", then this unsolicited AE will be categorized as "not within 30 days".

A few examples of missing time of onset with start date of AE partially missing:

		Start date of the AE	Injection date + 30	Will be analyzed
•	injection date			"Within 30 days"?
16Oct2023	16Oct2023	Missing	N/A	Y
16Oct2023	16Oct2023	Sep2023	N/A	N
16Oct2023	16Oct2023	Oct2023	15Nov2023	Y
16Oct2023	16Oct2023	Nov2023	15Nov2023	Y
16Oct2023	16Oct2023	Dec2023	15Nov2023	N
05Jan2023	05Jan2023	2022	N/A	N
16Oct2023	16Oct2023	2023	15Nov2023	Y
08Dec2023	08Dec2023	2024	07Jan2024	Y
16Oct2023	16Oct2023	2024	15Nov2023	N

Time of onset period is displayed as D1-D4, D5-D8, D9-D15, D16 or later, and Missing.

4.2.1.2.5 **Duration**

Duration is derived from the start and end dates of the unsolicited AE:

Duration = End date of unsolicited AE - start date of unsolicited AE + 1.

The duration is considered as missing only if one or both of the start and end dates of the unsolicited AE is missing or partially missing.

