## 8.3 Adverse Events (AEs), Serious Adverse Events, and Other Safety Reporting

The definitions of an AE, SAE, and the different categories of AEs can be found in Appendix 10.2.

AEs will be reported by the participants/participants' parents/legally acceptable representatives to the Investigator, then by the Investigator to the Sponsor.

The Investigator and any qualified designees are responsible for detecting, documenting, and recording events that meet the definition of an AE or SAE and remain responsible for following up AEs that are serious, considered related to the study intervention or study procedures, or that caused the participant to discontinue the study (see Section 7).

The method of recording, evaluating, and assessing causality of AEs and SAEs and the procedures for completing and transmitting SAE reports are provided in Appendix 10.2.

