3.4.4.1.4 Start Date and End Date

Missing or partially missing start dates or end dates for unsolicited AEs (including SAEs) will remain missing and not be imputed. If the start date is missing or partially missing, the time of onset will be considered to be missing. Nevertheless, unsolicited AEs with missing time of onset will be included in analyses within or not within the defined time window (according to the section 4.2.1.2.4), according to the last vaccination (computed according to the section 4.2.1.2.3). If either the start date or end date is missing or partially missing, the duration will be considered missing.

Missing or partially missing end dates for ongoing solicited AEs will remain missing and not be imputed.

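### The duration rule for unsolicited AEs pools events still ongoing at the last contact with events whose end date was lost, so any duration summary leans short (minor)

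*SAP*

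**What the plan says.** SAP 4.2.1.2.5 defines "Duration = End date of unsolicited AE - start date of unsolicited AE + 1". It adds that the "duration is considered as missing only if one or both of the start and end dates of the unsolicited AE is missing", or partly so. SAP 3.4.4.1.4 says the same under missing data: "If either the start date or end date is missing or partially missing, the duration will be considered missing". Neither section imputes an end date, derives a minimum or censors at the last contact. The SAP names a Missing display category for time of onset (4.2.1.2.4) but says nothing about how a Missing duration is shown.

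Solicited reactions that outlast the solicited period have a parallel rule in SAP 4.2.1.1.6: "If the end date is missing or incomplete (contains missing data), the overall number of days of presence will be considered as Missing". SAP 3.4.4.1.4 adds: "Missing or partially missing end dates for ongoing solicited AEs will remain missing and not be imputed". A separate variable, days of presence within the solicited period (SAP 4.2.1.1.5), needs no end date: "It corresponds to the number of days with daily intensities of Grade 1, Grade 2, or Grade 3".

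On follow-up, Protocol 8.3 has investigators "remain responsible for following up AEs that are serious, considered related to the study intervention or study procedures", together with AEs that caused discontinuation. Protocol 8.3.3 adds AESIs and follows all of these until they resolve or stabilize. Protocol 10.2.3 continues past the end of the study for AEs likely to be related, and the closing date goes to the Sponsor. Protocol 8.3.1 does not oblige investigators to look for further AE information once participation has ended.

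**The concern.** An absent end date can mean two things. The event may have resolved on a day nobody recorded, or it may not have resolved when the participant was last seen. The first is a lost value. The second is a right-censored value: the event lasted at least from its start to the last contact. The rule gives both the label Missing.

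The second kind is not a random subset. For a given onset day, the longer the event, the more likely it outlasts Visit 2. A duration table built from dated events therefore describes AEs that ended in time to be dated. Describing safety is one of the study's two objectives, and duration is among the characteristics that may be derived (SAP 3.4.3). If a duration table is produced, it should not lean in a known direction when the data to prevent this are already collected.

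**Working it through.** The plan gives no figure for AE duration or for the share of AEs without an end date, so there is nothing of the plan's own to reproduce on this point.

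**1. Observation time.** Unsolicited AEs are analyzed with onset on D1 to D31 (SAP 4.2.1.2.4). Visit 2 falls on D31 to D45 (D31 plus a window of 14 days). An AE starting on day s, with last contact on day V, can be observed for V − s + 1 days:
- onset D1: 31 days (V = 31) or 45 days (V = 45)
- onset D31: 1 day (V = 31) or 15 days (V = 45)

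**2. Who is affected.** Serious, related, discontinuation-causing and special-interest events have a route to an end date (Protocol 8.3.3, 10.2.3). Injection-site AEs and solicited systemic reactions count as related by convention (SAP 3.4.4.1.2). What remains is mainly non-serious unsolicited systemic AEs judged unrelated and ongoing at Visit 2.

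**3. Direction.** With no later follow-up, a duration D is Missing exactly when D > V − s + 1. That probability rises with D, so dated events are shorter than all events. Showing a Missing row does not remove the lean: each unresolved event belongs to some duration category but is counted in none.

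**4. Illustrative size for that group.** Assumptions, none from the documents: onset uniform on D1 to D31; duration exponential with mean parameter m, rounded up to whole days; no end date obtained after the last contact. With q = exp(−1/m):
- P(D > k) = q^k, and the true mean is 1/(1 − q)
- share without a duration = (1/31) × Σ q^k, with k = V − s + 1 and s = 1 to 31
- mean among dated events = Σ_k Σ_{d≤k} d·P(D = d) / Σ_k P(D ≤ k)

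For m = 7 and V = 31: q = 0.8669, and Σ q^k over k = 1 to 31 is 6.512 × 0.9881 = 6.434. Then 6.434/31 = 20.8%. For V = 45, k runs from 15 to 45, so multiply by q^14 = 0.1353: 2.8%.

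| m (days) | True mean | V=31: no duration | V=31: mean of dated (ratio) | V=45: no duration | V=45: mean of dated (ratio) | Over 7 days: true / dated V=31 / dated V=45 |
|---|---|---|---|---|---|---|
| 3 | 3.5 | 8.2% | 3.2 (0.91) | 0.1% | 3.5 (1.00) | 9.7 / 7.3 / 9.6% |
| 7 | 7.5 | 20.8% | 5.6 (0.75) | 2.8% | 6.9 (0.92) | 36.8 / 26.5 / 35.0% |
| 14 | 14.5 | 38.8% | 7.7 (0.53) | 14.3% | 10.4 (0.72) | 60.7 / 41.3 / 54.1% |
| 30 | 30.5 | 61.3% | 9.3 (0.31) | 38.4% | 13.4 (0.44) | 79.2 / 51.2 / 66.2% |

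If Missing is shown and all events form the denominator, then for m = 7 and V = 31 the over-7-days row reads 26.5% × (1 − 0.208) = 21.0%, beside 20.8% Missing. The true share is 36.8%.

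A simulation of the same set-up (1,000,000 events per scenario) agreed with these results. A Kaplan-Meier median censored at the last contact equaled the true median in every scenario (for m = 14: 10 days, against 6 and 8 days among dated events for V = 31 and V = 45).

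**5. Solicited reactions.** The formula in SAP 4.2.1.1.6 is right when an end date exists. A reaction present on all 8 days and ending on D10 gives (10 − 1) + 8 − 8 + 1 = 10 days. Elapsed time would be the wrong substitute when presence is broken. For a reaction present on D1 and D8 only and still present at a D31 contact, elapsed time is 31 − 1 + 1 = 31 days. The existing formula with D31 as end date gives (31 − 1) + 2 − 8 + 1 = 25.

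**The case against.** The case for leaving the rule alone has real substance.

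- **No event leaves the safety analysis.** An unsolicited AE counts if it has a verbatim term and is not Grade 0 (SAP 4.2.1.2.1), and outcome is summarized as collected (SAP 4.2.2.4). A reader might infer that ongoing AEs vanish from the tables; only their duration value does. This stands.
- **No mean or median duration is planned.** SAP Table 3.1 gives numbers and percentages for safety results, and duration is only an item that may be derived. A reader might take the ratios above as errors in a figure the sponsor will report; the SAP announces no such figure. This stands, but percentages by duration category shift in the same direction.
- **Missing durations may be displayed.** The SAP states it elsewhere when missing values leave a denominator (4.2.1.1.3, 4.2.1.1.7) and does not do so here. Display would help, but it would still mix unresolved events with lost dates.
- **Related and serious AEs are followed.** This stands and confines the point to the group in step 2. Even there, the protocol's duties are minimums, and a site may still record an end date.
- **Solicited reactions are hardly exposed.** They start by D8, at least 31 − 8 = 23 days before Visit 2. They also keep their D1 to D8 days of presence and a derived ongoing status (SAP 4.2.1.1.7). This stands; the solicited part is secondary.

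**Conclusion.** The point holds in a narrow form and is minor. For unsolicited AEs, the SAP does not separate a duration that is censored from one that is lost, and any duration summary or category percentage for the affected group leans short. The direction follows from the rule and the visit schedule. The size does not: it ranges from nil (short events, late Visit 2) to large (long events, Visit 2 at D31), and the table rests wholly on assumed onset and duration distributions and on no dating after the last contact.

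A reader might infer that the rule flatters the vaccine. The documents do not support that. The events mainly affected are those judged not caused by the vaccine, and vaccine-related ones are followed further. The study is single-arm and descriptive, with no hypothesis and no decision tied to AE duration.

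**What to change.** In SAP 4.2.1.2.5 and 3.4.4.1.4, for an unsolicited AE with a complete start date that is recorded as not resolved at the last contact:
- derive a minimum duration = last contact date − start date + 1;
- show it in a row for events ongoing at last contact, lasting at least n days, with its count;
- if a median is reported, censor the event at that date.

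Keep Missing for an unknown or partial start date, or a resolution on an unknown date, and show that count too.

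In SAP 4.2.1.1.6, only where a solicited reaction is confirmed ongoing at the last contact, put the last contact date in place of the end date in the existing formula and label the result a minimum. Do not use elapsed days from onset. The result keeps the formula's convention that every day after the solicited period counts as a day of presence.

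The cost is a few sentences, a small program change and one more row in the duration tables. The start, visit and outcome data are already collected. The change assumes that the outcome field identifies unresolved events; the CRF is not in the documents, so that should be checked.
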